## 7.6 Safety evaluation and Reporting by sponsor

The sponsor will ensure that all legal reporting requirements are met. According to GCP the sponsor is responsible for the continuous safety evaluation of the investigational product(s) and the clinical trial. The IZKS on behalf of the sponsor will conduct the management of SAEs and the expedited reporting in Germany as required by German Drug Law (AMG) and GCP regulation (GCP-V). Suspected unexpected serious adverse reactions (SUSARs) and safety issues as defined by GCP-V are determined for expedited reporting: The competent authorities and the ethics committees should be notified as soon as possible but not later than 15 calendar days, and 7 calendar days if it was fatal or life-threatening. All investigators will be informed within the same timeframe. The marketing authorization holder of the IMP should be informed too. Work flow and procedures concerning Safety management will be described in a separate document.

During the clinical trial the sponsor will submit the Development Safety Update Report (DSUR) including a list of all serious adverse reactions to the ethics committee(s) and the competent authorities once a year.

## 7.7 Immediate Reporting of pregnancy by investigator

Any **pregnancy** diagnosed in a female subject during treatment with the investigational product must be reported immediately using the "Pregnancy Reporting Form" to:

**IZKS Mainz  
[name]  
[name]  
[contact]**

Pregnancy occurring during the clinical trial, although not considered a SAE, must be reported within the same timelines as a serious adverse event. The outcome of a pregnancy should be followed up carefully and abnormal outcome of mother or child should be reported if any.

When the outcome of the pregnancy and the definite condition of the child could be established, the investigator completes the "Pregnancy Outcome Form", and faxes the completed Report Form II to IZKS.

## 7.8 Documentation of Abuse, Misuse, Overdose and Medication Error

All special events such as study medication abuse, misuse, overdose and medication errors including dilution errors and infusion rate errors have to be documented in the subject's CRF and source documents. If any abuse, misuse, overdose, or medication errors lead to an (serious) adverse event, then the event has to be documented and reported as AE/SAE.

## 7.9 Emergency procedures

During and following a subject's participation in the trial, the investigator should ensure that adequate medical care is provided to a subject for any AEs including clinically significant laboratory values.

Emergency treatment: see 4.2

Emergency unblinding: see 3.5.2

## 7.10 Other safety data

### 7.10.1 Previous and intercurrent illnesses

Illnesses already known at the time of informed consent are to be documented in the CRF as medical history. Illnesses detected during the clinical trial are to be documented as Adverse Events (see above).

### 7.10.2 Previous and intercurrent medical treatments

All medical treatments with the exception of the Investigational Medical Products received by the participant at the beginning and / or during the clinical trial are to be documented in the CRF as concomitant medication.

Routine physical examination and laboratory determination as specified above at study visits.

## 8 STATISTICS

Details of the statistical analysis of the data collected in this trial will be documented in a Statistical Analysis Plan (SAP) that will be generated by IZKS Mainz and finalized before closing the data base and prior to breaking the blind. The SAP is based on the protocol including all amendments. The document may modify the plans outlined in this protocol; however any major modifications of the primary outcome definition and/or its analysis will also be reflected in a protocol amendment. Any deviation from the original statistical plan must be described and justified in the final report. The statistical analysis will be conducted by means of SAS®.

### 8.1 Sample size

Due to the exploratory nature of the study there is no formal sample size calculation. The study aims to include 80 patients.

### 8.2 Analysis populations

All subjects with signed informed consent are considered as enrolled subjects, even if they did not receive any trial treatment. All randomised subjects will be included in the Intention-to-treat (ITT) population. This population is the primary analysis population. Within ITT population analyses subjects will be assigned to the treatment to which they were randomised. For the combined analysis the ITT Population consists of all patients that are at least in the START or the STOP block. The corresponding PP Populations consist of the patients from the ITT population without major protocol violations. Major protocol violations will be defined in the SAP. The safety population comprises all subjects who received at least one dose of trial treatment. In analyses of the safety population subjects will be assigned to the treatment which they actually received. The analysis populations will be defined prior to unblinding of the study.

For analysis, subgroups of patients will be defined, based on age, categories of diagnosis and further appropriate factors.

### 8.3 Efficacy analyses

The primary population for the analyses of efficacy are the ITT Populations (randomised patients) for each block. For the combined analysis the ITT Population consists of all patients that are at least in the START or the STOP block. For all hypotheses two-sided exploratory p-values will be provided.

If appropriate, the analyses will be adjusted for the stratification factor of the randomization: age group. The final efficacy analysis will be described in the Statistical Analysis Plan (SAP).

#### 8.3.1 Definition and analysis of primary outcome

The oxygenation of the patient is the primary outcome variable. The primary outcome will be assessed as the response rate of oxygenation to the intervention. As the patient's respiratory condition can vary over a broad range, may necessitate variable external support, and as these changes may occur over relatively short time periods, it is necessary to take all this into consideration when assessing oxygenation. Therefore we defined the parameters to be measured depending on the patient's condition to define a responder (Table 3.8-1). The majority of children included into the study are expected to be on supplemental oxygen or in room air. In these subjects oxygen saturation in room air will be assessed (for assessments please see 3.2). However to include the broad continuum of respiratory support possible in individual patients, an approach was chosen accommodating that need. Responses to treatment judged as significant were defined depending on Patient's condition. How and when to assess the variables is further detailed in the study protocol.

Oxygenation, the primary outcome parameter, was chosen as a dichotomous variable (response yes or no). Its components, i.e. O2-saturation and respiratory rate, are also used continuously in a descriptive manner as secondary outcome variables.

Tab 3.8-1: Definition of responders to treatment depending on Patient's condition

Patient's condition	Measured parameters	Specific metric	Definition of significant change or responder to the initiation of HCQ	Definition of significant change or responder to the withdrawal of HCQ	Method of aggregation
In room air	In room air O2 Sat (mean value) Respir rate (mean value)	Change from baseline	Increase $\geq 5\%$ in O2 Sat, or Decrease in resp. rate $\geq 20\%$	Decrease $\geq 5\%$ in O2 Sat, or Increase in resp. rate $\geq 20\%$	Proportion of responders
On O2-supplement	In room air O2 Sat (mean value) Respir rate (mean value)	Change from baseline	Increase $\geq 5\%$ in O2 Sat or Decrease in resp. rate $\geq 20\%$ or Support no more needed	Decrease $\geq 5\%$ in O2 Sat, or Increase in resp. rate $\geq 20\%$ or Support newly needed	Proportion of responders
On high-flow nasal cannula	O2-flow, air-flow	Change from baseline	Decrease $\geq 20\%$ or Support no more needed	Increase $\geq 20\%$ or Support newly needed	Proportion of responders
Ventilated	Oxygenation index	Change from baseline	Decrease $\geq 20\%$ or Support no more needed	Increase $\geq 20\%$ or Support newly needed	Proportion of responders

The definition of the threshold for a significant change or responder regarding oxygenation will be further assessed as a secondary outcome.

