h Health economics assessment with the use of a special questionnaire which has to be filled out by the parents or adult patients.

i Quality of Life assessment with the use of the questionnaire PedsQL for different age groups which has to be filled out by parents and/or patients

j For Electrocardiography (ECG), ophthalmological review and Echocardiography (Echo) please see Chapter 5. If a routine ophthalmological examination was done within 3 month before Visit 1, no additional ophthalmological exam is required.

k Pregnancy test only has to be performed in girls of childbearing age and only if sexual relations are known or probable. It is at the discretion and responsibility of the attending physician to decide, whether a pregnancy test is necessary or not. The pregnancy test can be performed in the urine or serum.

l The following parameter will also be assessed, if there is **oxygen demand**:

1. O2 via nasal cannula or via face mask: O2-Flow (l/min)
2. on high-flow nasal cannula: Flow air (l/min), O2-Flow (l/min), FiO2

m The following parameter will also be assessed on ventilation: ventilation method, duration of ventilation (hours/day/only for non-invasive ventilation), PEEP (cmH2O), PIP (cmH2O), FiO2, Ti (sec), MPAW (cmH2O) and Oxygenation Index (OI);  
In addition, if patients on the heart lung machine (e.g. NO (%), ECLS (VV/VA/ECLA), Flow/time since insertion) will be documented descriptively.

n Calculation of Oxygenation Index (OI): OI = (FiO2 \* MPAW)/PaO2

with MPAW = ((frequency \* inspiration time)/60) \* ((inspiratory pressure (PIP) – PEEP) + PEEP)); If PaO2 is not available, PcapO2 can be used.)

o Start date, End date, Patient returned to baseline function? Y/N

1. Increase in respiratory rate? Y/N/not done.

2. Increase or development of dyspnea ? Y/N

3. Newly developing or increased abnormalities on chest imaging ? Y/N/not done

4. Onset/increase of oxygen demand to attain the individual baseline saturation ? Y/N

5. Need for an additional level of ventilatory support (in addition to oxygen) ? Y/N

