6.6 Primary Analysis

The variable assessing the primary outcome is the response rate measured by the oxygen saturation in room air.

START HCQ block

Relative change from trial day 1 (Visit 2) to day 28 (Visit 3) and day 56 (Visit 4) and from day 28 to day 56 change from active compound compared to change from placebo

STOP HCQ block

Relative change from trial day 1, i.e. Visit 2, through day 84, i.e. Visit 5: change from active compound compared to change from placebo

Both blocks separately

a) A difference between the changes in placebo and active phases is considered significant as described in the table below.

Patient's condition	Measured parameter	Definition of significant change or responder
Stable in room air or on	SpO2 in room air	Increase $\geq 5\%$

O2-supplement		
On high-flow nasal cannula	O2-flow, air-flow	Decrease $\geq 20\%$ or support not needed any more
Ventilated	Oxygenation index	Decrease $\geq 20\%$ or support not needed any more
On ECMO		Decrease $\geq 20\%$ or support not needed any more

The analysis will be done first by discarding the information on the patient's condition. Descriptive analyses will be done overall and for all patients conditions separately.

b) Patients are defined as responder as described in the table above. The numbers of responders are counted and compared by Fisher's exact test as well as logistic regression models with factors for treatment group and age group.

The following SAS code can be used:

```
PROC LOGISTIC DATA=indata;
  CLASS treatment age_gr;
  MODEL responder_YN = treatment age_group treatment*age_group;
RUN;
```

Both blocks together

Not applicable. There were too few patients in both blocks.

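### In the STOP block, new need for respiratory support is not an event criterion for a child in room air, the time point that defines the row is unstated, and the SAP's responder table counts no worsening at all

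*Protocol*

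**What the plan says.** Protocol 8.3.1 makes the primary outcome a yes/no response, judged as change from baseline, with criteria that depend on the patient's condition. Tab 3.8-1 has one column for starting HCQ and one for withdrawing it.

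- Room air, withdrawal column: "Decrease $\geq 5\%$ in O2 Sat, or Increase in resp. rate $\geq 20" per cent. The clause "Support newly needed" is absent from this row.
- On oxygen, withdrawal column: the same two criteria, ending "Increase in resp. rate $\geq 20\%$ or Support newly needed".
- High-flow and ventilated, withdrawal column: "Increase $\geq 20\%$ or Support newly needed", applied to the flows and to the oxygenation index respectively.
- On oxygen, initiation column: the counterpart wording is "Decrease in resp. rate $\geq 20\%$ or Support no more needed". The high-flow and ventilated rows carry the same support clause.

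The protocol does not say at which time point the row is fixed, or how to classify a child who changes row between Day 1 and Day 84.

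SAP 6.6 has one table for both blocks, with a single criterion column headed "Definition of significant change or responder". Every entry is an improvement: SpO2 up by at least 5% for children in room air or on oxygen, and otherwise a fall of at least 20% or support no longer required. The statistical section of the protocol synopsis likewise describes only a rise in saturation, for both blocks.

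**The concern.** In the initiation column, loss of support sits in the three rows where a child has support to lose. The withdrawal column mirrors that wording in the same three rows. The room-air child, for whom any support would be new, is left without the criterion.

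Protocol 3.3 and 8.3.1 both say that oxygenation has to be judged in the light of the support given, and 8.3.1 expects most children to be in room air or on oxygen. The protocol also treats new oxygen need as a sign of deterioration elsewhere: item 4 of the exacerbation footnote to the trial schedule is "Onset/increase of oxygen demand to attain the individual baseline saturation". Going onto oxygen after HCQ is withdrawn is the kind of change the STOP block is meant to detect. Whether it counts in the primary outcome should not depend on how an analyst reads a row label.

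**Working it through.** The plan gives no event rate, power or sample-size formula for this endpoint, so there is no stated figure to reproduce. The check is a reading of the table, then arithmetic on the thresholds, then an illustration under assumed rates.

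**1. The table, with the row read as the Day 1 condition**

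| Row | Support clause, initiation | Support clause, withdrawal | Consequence in STOP |
|---|---|---|---|
| Room air | none | none | starting any support is not itself an event |
| On oxygen | no longer needed | newly needed | works only if it means a higher level; not defined |
| High-flow | no longer needed | newly needed | same |
| Ventilated | no longer needed | newly needed | same |

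**2. What a room-air child must do to count**

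SpO2 is still read in room air for a child on oxygen, after oxygen is taken off (Protocol 3.3, Tab 3.3-1). The value is therefore comparable with Day 1, and the test is a fall of at least 5% or a rise in respiratory rate of at least 20%.

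- Baseline 94% (assumed), relative threshold: 94 × 0.95 = 89.3%.
- 94 to 90: 4/94 = 4.26%, below 5%; also 4 points, below 5 points.
- 92 to 88: 4/92 = 4.35%. 90 to 86: 4/90 = 4.44%.
- A fall of 5 points: 5/98 = 5.10% up to 5/85 = 5.88%, so it qualifies.

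For baselines of 85% to 98%, a 4-point fall fails and a 5-point fall passes whether the 5% is read as relative or absolute. The uncounted group is children newly on oxygen with a smaller fall than this and a respiratory-rate rise under 20%. The documents give no saturation at which oxygen is started, so these examples are assumptions.

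**3. A child who moves to high-flow or ventilation**

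Tab 3.3-1 assigns flows or the oxygenation index to these conditions. A child in room air on Day 1 has no baseline value of either, so a 20% change cannot be formed. The room-air row has no support clause to fall back on, and no rule covers the change of row.

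**4. What the SAP does with the same child**

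Under SAP 6.6 a STOP child in room air or on oxygen is a responder only if SpO2 rises by at least 5%. Respiratory rate is not in that row. As an assumed case, a fall from 94% to 84% (10/94 = 10.6%) is classified exactly as no change. No worsening of any kind enters the Fisher test or the logistic model as an event.

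**5. Sensitivity of the comparison (illustration only)**

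The planned 80 patients, split equally between blocks and randomised 1:1 (Protocol 3.2, 3.5.1, 8.1), give 80/2/2 = 20 per arm in STOP. Assumed: two-sided Fisher test at 0.05 (the plan sets no alpha), event rates on placebo and HCQ as shown, and the same share of events missed in both arms.

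| Placebo vs HCQ | none missed | 20% missed | 50% missed |
|---|---|---|---|
| 30% vs 5% | 0.45 | 0.31 | 0.11 |
| 40% vs 10% | 0.49 | 0.36 | 0.17 |
| 50% vs 10% | 0.74 | 0.58 | 0.30 |

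The rates behind the second row are 0.40 × 0.8 = 0.32 vs 0.10 × 0.8 = 0.08, and 0.20 vs 0.05. One uncounted placebo event can also matter: 7/20 vs 1/20 gives p = 0.044, and 6/20 vs 1/20 gives p = 0.092.

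**The case against.** The best defence is that each row names the support in question rather than the Day 1 state. In START that support is dropped; in STOP it is taken up. The support clause is joined by an or, so it needs no comparable baseline value. On this follow-up reading a room-air child who ends on oxygen, high-flow or ventilation falls in the matching row and counts. This is a workable reading of the protocol table. But the protocol does not state it. It would require the same row label to mean Day 1 condition in one column and follow-up condition in the other. It also does nothing for SAP 6.6, which has no withdrawal column.

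A reader might infer three stronger things that the documents do not support:

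- *Every child who becomes oxygen-dependent is missed.* No. Room-air SpO2 and respiratory rate are still measured, and a change that reaches either threshold counts.
- *New need for support is impossible for a child already on support.* No. A child on oxygen can newly need high-flow or ventilation, and the exacerbation items list an additional level of ventilatory support separately. The clause is undefined in those rows, not empty.
- *A child escalated to ventilation is dropped under SAP 5.1.* That section says only that missing values are not substituted. The STOP schedule lists room-air saturation at every visit, with the oxygenation index as an addition for ventilated patients. The child is unclassified; exclusion is an inference.

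It is also fair that oxygen demand and exacerbations are protocol secondary outcomes and that the trial is exploratory. The information would therefore be reported, but outside the primary outcome.

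**Conclusion.** The point holds as an unresolved definition in the protocol and a wrong direction in the SAP. With the row taken as the Day 1 condition, a room-air child who starts oxygen below both thresholds is a STOP non-event, and one who moves to high-flow or ventilation has no stated classification. Under the SAP as written the gap is wider, because no deterioration counts for any child in STOP.

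How many events are affected is unknown. The documents give no event rates and no share of children who would start support below the thresholds. The power figures show only that about 20 per arm leaves little room for lost events; they are not an estimate of the loss. It would go too far to say that the protocol rule demonstrably under-counts, since that depends on the baseline reading, which fits the change-from-baseline metric but is not stated.

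**What to change.** 1. In Protocol 8.3.1, state that the row is the patient's condition on Day 1 (Visit 2).
2. In the withdrawal column, add new need for support to the room-air row. In the oxygen, high-flow and ventilated rows, define the clause as a step up to a higher level of support than on Day 1, in the order room air < oxygen < high-flow < ventilated < ECMO. Count it as an event whether or not the Day 1 parameter can still be measured.
3. Put this STOP-specific worsening table into SAP 6.6 beside the START table, so that the STOP analysis compares proportions who worsen, and bring the synopsis into line.
4. Make the change before unblinding and issue the protocol amendment that section 8 requires for a major modification of the primary outcome. A later change would have to be described and justified in the final report as a deviation.

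The cost is table wording in two documents and the programming of one derived variable. Oxygen demand and the ventilation items are already scheduled at every STOP visit. Only endpoint classification changes; clinical care does not.

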#### Controlled initiation of HCQ

Relative change trial day 1 (i.e. Visit 2), through day 28 (i.e. Visit 3) and relative change day 28 (i.e. Visit 3) to day 56 (i.e. Visit 4) active compared to change placebo

#### Controlled withdrawal of HCQ

Relative change trial day 1 (i.e. Visit 2) through day 84 (i.e. Visit 5): change active compound compared to change placebo

### 8.3.2 Analysis of secondary outcome

All analysis of secondary outcome will be interpreted purely exploratory. Continuous and quasi-continuous variables will be displayed by the descriptive statistics: N (number of observations), mean, standard deviation, minimum, median, maximum and the number of missing observations. Categorical variables will be displayed by absolute and relative frequencies. Exploratory p-values will be calculated when appropriate. Time to event data will be displayed by Kaplan-Meier Plot when a reasonable number of events occur.

### 8.3.3 Analysis of Subgroups

If appropriate, subgroups will be defined in the SAP.

### 8.3.4 Interim analyses

No interim analyses are planned.

## 8.4 Analysis of adverse events

All summaries and listings of safety data will be performed for the safety population.

Frequencies of subjects experiencing at least one adverse event (AE) will be displayed by body system and preferred term according to MedDRA terminology. Detailed information collected for each AE will include: A description of the event, duration, whether the AE was serious, intensity, relationship to trial drug, action taken, clinical outcome. Summary tables will present the number of subjects observed with AEs and corresponding percentages. Additional subcategories will be based on event intensity and relationship to trial drug. A subject listing of all AEs will be prepared.

## 8.5 Analysis of clinical laboratory findings

Listings will be prepared for each laboratory measure and will be structured to permit review of the data per subject as they progress on treatment. Summary tables will be prepared to examine the changes of laboratory measures over time. Additionally, shift tables will be provided to examine the changes of laboratory data from normal baseline to values outside the corresponding reference range during/after treatment.

## 8.6 Other

Steady state drug levels and ECGs will be monitored. Ophthalmologic exams will be done.

# 9 QUALITY CONTROL AND QUALITY ASSURANCE

## 9.1 Requirements for investigational sites and staff

The investigator should be able to demonstrate (e.g. based on retrospective data) a potential for recruiting the required number of suitable subjects within the agreed recruitment period. The

investigator should have sufficient time to properly conduct and complete the trial within the agreed trial period. The investigator should have available an adequate number of qualified staff and adequate facilities for the foreseen duration of the trial to conduct the trial properly and safely. The investigator should ensure that all persons assisting with the trial are adequately qualified, informed about the protocol, any amendments to the protocol, the trials treatments, and their trial-related duties and functions.

